9.2.1 Materials for Swab Collection for Resistance Testing

Swabs

NP specimens will be collected using sterile, individually-wrapped pediatric flocked swabs with a plastic swab shaft (manufactured by Copan). Nasal sites will be swabbed with a sterile, Dacron polyester-tipped swab with a plastic shaft (manufactured by Fisherbrand).

Sample Tubes

All field samples for DNA testing will be collected into sterile 2.0ml microcentrifuge tubes, manufactured by Sarstedt®. (DNA-free tubes will be used for collection in DNA/RNA shield.)

Cooler Bags with Frozen Ice Packs

Insulated cooler bags will be used to carry samples to and from the field. In addition, frozen gel ice packs designed to thaw slowly will be used to maintain the temperature in the cooler bags during transport.

-20°C Freezer

A standard -20°C freezer located at the local health center will be used strictly for the storage and freezing of ice packs and samples. This freezer is kept in a locked room on the grounds of the Health Center, which is under 24-hour security guard supervision.

9.2.2 Protocol for Tubing and Handling of Samples

The tubing and handling protocol must be carefully followed in order to prevent contamination and ensure the safe transport of the samples back to the local microbiology laboratory and/or to the US for processing. The person in charge of labeling, tubing, arranging, and handling the samples needs to perform this task in the most orderly and attentive manner.

1. Both hands of the tuber should be gloved at all times. The tuber's gloves only need to be changed when any potential contamination of the gloves occurs. The tuber opens the capped, hinged lid of a microcentrifuge tube, which has been labeled with the participant's random identification number.
2. The swab is inserted by the examiner into the microcentrifuge tube held by the tuber. The swab shaft should only be inserted until the swab head is fully in the tube. The tuber will cut the swab shaft with sterile scissors.
3. The tuber should screw the cap of the microcentrifuge tube tightly, flick the tube to mix the sample with the media (for tubes with DNA/RNA shield media), and place it in the sample collection box, located in the cooler bag filled with frozen ice packs. The flap of the cooler bag should be closed between each patient. The cooler bag should be in as cool a place as possible in the field, in a shaded area out of the sun.

Upon returning from the field each day, the samples in STGG will be immediately taken to a local health center and stored in a commercial -20°C freezer, reserved solely for storage of specimens and ice packs. All samples will be in sample boxes, labeled with the village name for easy future identification.

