3.1. Randomization

Randomization of Treatment Allocation. In each site, communities within a contiguous area of 300,000 to 600,000 individuals will be randomized to azithromycin or placebo for the mortality study. An additional 30 communities will be randomized into one of two study arms for embedded, cost-efficient, morbidity studies. Since mortality and morbidity study communities will be drawn from the same pool, findings from one study will be relevant to the other. Each site has a different set of prevalent co-morbidities and different access to health interventions.

No stratification or block randomization is planned within each country. The allocation of community assignments will be conducted for each country separately using simple random sampling. For each country, all study arms (mortality and morbidity) will be assigned from the same list of eligible communities. A pseudorandom number scheme will be implemented using the statistics package R. Randomization will be conducted by [name]. Procedural and algorithmic details are provided in an appendix to the Statistical Analysis Plan.

Study Participants: At months 0, 12, and 24, a random sample of children will be selected using a computer-generated simple random sample for exams and sample collection to monitor for morbidity and resistance.

Chapter 4: Study Eligibility

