12.1 De-identification

All specimens will be labeled in the field with a random identification number linked to the census in the electronic data capture system, but to facilitate masking, only the DCC will have access to the key linking the ID with census information. Age, gender, and community of residence will be available for each specimen, but names will be kept confidential. Therefore, all specimens will be de-identified.

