12.4 Catalog Specimens

We will create a list of study data and specimens, including the age, gender, village identification number, treatment assignment, whether treatment was received, vaccination record, and symptom questionnaire. We will also list the date of collection and transport, and the storage conditions while in the field and while banked at UCSF. This will facilitate identification of specimens for future analyses.

Chapter 13: Microbiology and Molecular Laboratory Procedures

Participant names will not be included in laboratory records and samples will be de-identified. Therefore, laboratory personnel will be masked, preventing identification of the individuals infected. Lab results will not be available for weeks, if not months. Thus, all individuals will be treated according to their study arm, whether or not their lab tests reveal evidence of infection.

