13.3 Methods for Resistance Testing

13.3.1 Isolation & Identification of Organisms Using Microbiological Techniques

Various organisms from nasal, nasopharyngeal, and rectal swabs will be isolated using the media and conditions in Table 2 and identified using the methods summarized in Table 3 and below. Standard microbiological handbooks should be referenced for more detailed information.

Procedure for Masking Samples

The microbiologist and all lab staff will be masked to the community of origin.

Laboratory Results Reporting

All lab results will be kept in computer files as well as in hard-copy form by the Microbiologist.

Table 2. Isolation of Organisms from Source - Primary Plating Media & Incubating Conditions

Source	Media	Incubation	Organisms Isolated
Nasal Swab	Blood and MSA	35°C 5% CO ₂	S. aureus (core)
Nasopharyngeal Swab	Blood and Strep select plate, chocolate, chocolate with bacitracin	35°C 5% CO ₂	S. pneumoniae (core) H. influenzae (non-core) N. meningitidis (non-core)
Rectal Swab	Blood and MacConkey	35°C	E. coli (core)

Table 3. Identification of Organisms

Organism	Stain	Identification Tests
S. aureus (core)	Gram stain	Catalase and Tube Coagulase or latex agglutination reagent
S. pneumoniae (core)	Gram stain	Catalase, Optochin disc and/or Desoxycholate reagent, alpha-hemolytic on blood agar
H. influenzae (non-core)	Gram stain	Satelliting growth on blood agar, ALA or other identification tests
N. meningitidis (non-core)	Gram stain	Sugars utilization or other identification kit
S. pyogenes (core)	Gram stain	Catalase, beta-hemolytic on blood agar, and Bacitracin disc or PYR test
E. coli (core)	Gram stain	Indole, oxidase, beta-hemolytic on blood agar, PYR and other identification tests as required

Description of Identification Tests:

We will follow the standard quality control methods already in place at the laboratory. For example, lab staff will perform positive and negative growth controls for all media, and positive controls for all stains and identification tests at a pre-determined schedule.

Catalase Test:

A few drops of 3% hydrogen peroxide are added to colonies removed from agar and smeared onto a clean glass slide, and immediately observed for the release of oxygen or “bubbling.” Bubbling is interpreted as the presence of catalase. Lack of bubbling is a negative test.

Tube Coagulase:

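### Village-named swab boxes in section 9.2.2 conflict with the protocol's own rule that resistance laboratory staff be masked to community, and no coding step resolves the conflict

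*Protocol*

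**What the plan says.** Section 9.2.2 of the Protocol belongs to 9.2, on nasopharyngeal swabs; its materials list (9.2.1) also covers nasal swabs. Each swab goes into a tube "which has been labeled with the participant's random identification number". After the step that moves STGG specimens to the health-center freezer, the section states: "All samples will be in sample boxes, labeled with the village name for easy future identification".

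Other sections bear on who may know the village:

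- Section 13.3.1, for organisms grown from nasal, nasopharyngeal and rectal swabs: "The microbiologist and all lab staff will be masked to the community of origin".
- Section 12.3.1: specimens bear nothing but the study ID and cannot be identified without the database.
- Section 12.1: the DCC alone holds the key from ID to census, but "Age, gender, and community of residence will be available for each specimen, but names will be kept confidential". It does not say to whom.
- Section 12.4: "We will create a list of study data and specimens, including the age, gender, village identification number, treatment assignment". The stated purpose is: "This will facilitate identification of specimens for future analyses".
- Section 13.4.3: conjunctival swabs receive a separate laboratory number, distinct from the child's random number, so that location is hidden until processing is finished.

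The unit of allocation is the community. Section 3.1 says: "An additional 30 communities will be randomized into one of two study arms for embedded, cost-efficient, morbidity studies".

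**The concern.** A random number on the tube hides the child. It does not hide the cluster if the tube sits in a box bearing the village name, and the cluster is what was randomised. The masking rule in 13.3.1 cannot then be met unless someone removes that name before the bench, and no one is assigned to do so.

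Emergent macrolide resistance is Objective 4, and nasopharyngeal resistance is a core element at all three sites. Under 13.3.2, inhibition zones are measured by hand and E-test values are read where the ellipse meets the scale, so borderline isolates call for judgement. The morbidity communities are sampled at months 0, 12 and 24. A reader who sees the village name could recall its earlier results and lean towards them. If resistance already differs by arm at month 12, that habit could track arm at month 24 even though the reader never learns the allocation.

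**Working it through.** The plan gives no figure to reproduce, so the check sets the passages side by side.

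1. **Does the label reach the laboratory?** Section 9.2.2 gives its purpose as safe transport to the local microbiology laboratory or to the US. The box sentence directly follows freezer storage at the health center. Section 12.2, on transport, mentions no re-boxing. The documents therefore do not say that the named box arrives at the bench, and do not say that it is replaced.

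2. **Which specimens?** The sentence speaks of all samples but stands in the nasopharyngeal part and follows the STGG step. STGG is the medium from which live bacteria are recovered; DNA/RNA Shield lyses cells (13.1.1, 13.1.2). The label therefore falls chiefly on swabs that can be cultured. Rectal and stool instructions (9.3.1) use a random-number label or a labeled tube and an ordinary sample box, with no village name.

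3. **Is a random tube number treated as enough?** Chapter 13 infers masking from the absence of participant names. Section 13.4.3 does not rely on this for conjunctival swabs: it adds a second number expressly to hide location. No counterpart is written for resistance swabs.

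4. **How many specimens?** Inputs: 40 children per community (5.2.1) and 30 communities per site, 15 per arm (3.1 and the schedule table in 4.3). 40 x 30 = 1,200 nasopharyngeal swabs per site at each core visit. This is an upper limit for culture in this age group, because a site may use DNA/RNA Shield instead of STGG.

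5. **When would this bias the comparison?** Let d_j be the reading error that village j contributes to its proportion resistant.
   - Estimated arm difference = true difference + (mean d_j, azithromycin) − (mean d_j, placebo).
   - If d_j is unrelated to arm, with variance s², the expected shift is zero. Variance rises by s²/15 + s²/15 = 2s²/15, about 0.133 s² per site. A community-level comparison already reflects this.
   - If the mean of d_j differs between arms, the estimate shifts by that difference, and more swabs per village do not reduce it.
   - The documents supply neither s² nor any between-arm difference in d_j, so the shift cannot be sized.

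6. **Does the SAP settle it?** Its resistance comparison states no laboratory masking. The primary rectal outcome there is sequencing reads from community pools, which leaves little to a reader's eye. The nasopharyngeal analysis is at community level and names no assay.

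**The case against.** The strongest reply is that the plan already requires masking. Section 13.3.1 says so outright, Chapters 7 and 13 repeat that laboratory personnel are masked, and 12.1 confines the linking key to the DCC. The box sentence may describe freezer storage only. This stands in part: the documents do not show that reading is unmasked. It does not remove the conflict, because the only labelling step written for these boxes points the other way.

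Four stronger readings are tempting, and the documents do not support them.

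- *That laboratory staff learn treatment assignment from the specimen list.* The list in 12.4 serves later use of banked specimens, and no text gives it to those reading plates. What remains is the need for a rule on access and timing.
- *That knowing the village means knowing the arm.* The control is placebo and drug is issued by treatment letter. Section 14.8 puts the letter in the field team's app, and no passage gives laboratory staff the letter or its meaning.
- *That every specimen type is affected.* Section 9.3.1 names no village on rectal or stool boxes.
- *That the arm difference is shifted by a given number of points.* This presupposes misreading that differs by arm, which is the very matter in doubt.

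It is also fair that a second number on each tube would not cure a named box; the box itself has to be coded. Resistance-gene PCR and sequencing leave less room for reader judgement than culture, and zone diameters are compared with fixed CLSI tables, which narrows the room further.

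**Conclusion.** The concern holds as an unreconciled conflict. Section 9.2.2 puts the name of the randomised unit on the swab boxes, while 13.3.1 requires staff not to know it and 12.3.1 says only a study ID is carried. With no coding step before the laboratory, masking to community is not secured for culture-based resistance results.

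The risk is loss of community masking. Bias in the arm comparison would follow only if allocation also became known or if reading drifted with arm. Its size cannot be stated; the 1,200 swabs per site per core visit measure exposure only. The conclusion assumes that boxes travel as labelled, which the documents neither confirm nor exclude. It does not touch the mortality outcome. It should be corrected because it concerns a core outcome, the masking rule is the protocol's own, and the remedy is nearly free.

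**What to change.** - **9.2.2:** replace the village name with a random box code issued by the DCC, new at each visit so that a reader cannot link a box to earlier results. Keep the code-to-village key at the DCC.
- **9.3.1:** apply the same box coding to rectal and stool specimens, so that one rule covers all resistance samples.
- **13.3.1:** refer to the coded boxes as the means by which community masking is achieved, bringing it into line with 12.3.1.
- **12.1 and 12.4:** state that neither community nor treatment assignment is released to laboratory readers until that visit's results are locked.

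The existing random number on the tube can stay as it is. Pooling by community for sequencing can use the box code. The cost is printed codes, short edits to five sections, and a DCC look-up whenever a box must be traced.

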9.3 Stool Samples

All study sites will collect either stool samples or rectal swabs for resistance testing, but methodology will depend upon the type of samples collected and consist of either culturing/microbiological testing or nucleic acid based testing.

Rectal Swabs for Culturing/Microbiological Testing

Rectal swabs will be collected and placed into Amies transport media or Norgen Stool Preservative. We will use standard microbiologic techniques to isolate

Escherichia coli. Resistance to azithromycin, ampicillin, and co-trimoxazole will be determined. Isolates can be further classified into commensal and diarrheagenic subtypes using a multiplex PCR assay.⁴³

Stool Samples for Nucleic Acid Based Testing

Stool specimens will be used to look for the presence of *E. coli* and macrolide resistant determinants typically associated with resistant strains of *E. coli*, using a resistome approach. This will be carried out by isolating DNA from stool specimens and detecting the presence of *E. coli* as well as genes associated with antibiotic resistance (i.e. *erm*, *mef*, and *mph* genes) via PCR assays.⁴⁵ Other possible experiments may eventually include using PCR to detect the presence of toxins or virulence factors (i.e. *eae*, *stx*, *bfp-A*, *VT-1*, *VT-2*), which are linked to diarrheagenic *E. coli* strains,⁴⁶⁻⁴⁷ or exploring the complete microbiome of the stool specimens.

9.3.1 Stool Specimen Collection

Rectal Swab Collection for Culturing/Microbiological Testing

The test will require that the child's parent and examiners work together to obtain a good sample. Is it important to describe the test to the parent so that they can best assist with keeping the child still during the procedure, if necessary.

In place of stool specimens, rectal swabs can be collected in the following way:

1. Put on a clean pair of gloves.
2. Partially open the fecal swab package and remove the top section of the collection vial (this can be discarded).
3. Position the child:
 - Lie the child on his/her back, hold legs in the air (it is useful to have assistance).
 - Or have the child lay on his/her stomach across the mother/guardian's lap
4. Remove the swab from the package. Take care that the cotton tip is not touched. If it is touched, throw the swab away and begin with a new one.
5. Insert the tip of the swab into the child's anus only as far as needed to contact fecal material (1-3cm) and rotate 180 degrees. The tip should be a brownish color when removed.
6. Place swab into the preservative in the collection tube. Make sure the swab is fully submerged in the liquid preservative and then break the swab off using the pre-scored breaking point.
7. Screw the cap back on the tube and make sure that it's tightened. Wrap the area where the cap meets the tube with Parafilm to ensure that the

sample will not leak, and then place the tube into the appropriate sample box.

- If the swab cannot be broken off while the tip is fully submerged in the liquid, try twirling the swab in the liquid first (to release the contents of the sample into the preservative) before breaking it off. Avoid rubbing the sample on the tip of the swab off on the side of the tube where there is no liquid.

8. Place a random number label on the collection tube.
9. Place the tube the rectal swab container.
10. **Swab storage for Genetic analysis:** Store samples at room temperature. According to the manufacturer, the preservative in the tube will preserve DNA for 5 months at room temperature (7 days for RNA), and thereafter can be frozen (-20°C or -80°C) for long-term storage.

Stool Specimen Collection for Nucleic Acid Based Testing

For the study participant/ parent of the child:

1. Collect the initial stool specimen on a piece of plastic.
2. Transfer a few heaping spoonfuls of the fresh stool into the smaller, 4 oz disposable plastic container that has a locking lid, using the spoon provided. Return this to the trained field worker.

For the trained field worker:

1. Wearing fresh gloves, carefully place a portion of the stool sample from the disposable 4 oz plastic container into a labeled Norgen Stool Nucleic Acid Collection and Transport Tube (15 ml collection tube that contains preservative), using the small spatula that is attached to the tube's cap. Fill up to the line as indicated by the tube.⁴⁴ Make sure to spoon the stool into the tube without touching the rim or outside of the tube to avoid any contamination.
2. Once the stool sample has been added, place the cap tightly back onto the tube.
3. Mix gently until the stool is well submerged under the preservative. Do not shake the tube up and down, just gently swirl.
4. Wrap the lid of the tube with a piece of Parafilm to seal it.
5. Place the tube into the storage box and store at room temperature.
6. Once the final stool sample has been collected in the Norgen Stool Nucleic Acid Collection and Transport Tube, wrap up the initial stool sample in the large receptacle container using the plastic lining and properly dispose of it. Also, dispose of the stool sample in the 4 oz plastic container and the spoon that was used.

9.3.2 Materials for Stool Specimen Collection

Rectal Swab Collection for Culturing/Microbiological Testing Swab

An individually-wrapped Copan flocked swab with a plastic shaft will be used to collect the rectal swab and then placed into a Stool Nucleic Acid Collection and Transport Tube containing Norgen Stool Preservative or Amies Transport Medium.

Sample Tube with Media

The specimen will be in a sterile Stool Nucleic Acid Collection and Transport Tube containing Norgen Stool Preservative or Amies Transport Medium with a cap that will be tightened firmly.

Stool Specimen Collection for Nucleic Acid Based Testing

Plastic Lining

Each participant will be given a piece of plastic that will be placed on the ground to collect the initial stool sample.

Spoon

Wooden medical spoon used to transfer a portion of the initial stool specimen to the small plastic container, which will be brought to the trained field worker by the parent.

Small Plastic Container

4 oz disposable plastic container with locking lid used to transport a portion of the initial stool specimen to the trained field worker.

9.4 Quality Control Measures for Specimen Collection

Negative Field Controls

Negative field control swabs for NP and stool will be taken in each community to assess for contamination: one control swab each (NP and stool/rectal) are taken before specimen collection begins in a community; and another (NP and stool/rectal) upon completion of specimen collection.

1. For each negative field control, the examiner will open a new swab as described above.
2. Wave the swab in the air, without making contact with anyone/anything.
3. Tube the swab in media, as described above.

Duplicate swabs

Duplicate NP swabs and rectal swabs/stool specimen will be collected from two children per community.

Chapter 10: Cost-Effectiveness

10.1. Costs

We will record the costs of distributions in a random subset of 12 villages at MORDOR 6 *or* 12 and MORDOR 24. We will assume a societal perspective. Programmatic costs will be included, such as: azithromycin, antibiotic distributors, supervisors, drivers, fuel, and the time of community volunteers, and the costs of azithromycin will be estimated using the market price for generic formulations. See appendix for the study forms to be used. Collection of certain costs will be incorporated into the electronic data capture system, including the duration of time that the antibiotic distributors worked, the number of antibiotic distributors per team, the number of doses of azithromycin/placebo given, and the number of doses of azithromycin/placebo wasted. Other costs will be collected on paper forms from the appropriate parties: the drivers will complete paper forms describing costs of fuel and automobile maintenance, and the study coordinator will complete paper forms describing the costs of consumables purchased for the study, as well as the overhead costs of maintaining the mass drug administration office.

